## ***6.3 Withdrawal criteria***

Patients may be discontinued from the study at any time. Specific reasons for discontinuation can be;

- Every subject is free to drop-out of the study at any time. These subjects will receive contraceptive counseling and treatment according to local routines and will suffer no negative consequences
- Serious adverse events
- Post abortion infection between randomization and planned insertion

Women who discontinue due to side effects or adverse events will be asked permission for follow up for a total of 12 months post abortion.

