### 3.3 Ethical considerations

There is strong evidence that an unintended pregnancy is a potential risk for poor fetal outcome, poor quality relationship between the mother and the child, and adverse effects on mental health (16, 17). A repeat abortion may entail small health risks.

If the results of the study can show that early insertion is superior to standard procedure

concerning use, patient satisfaction and safety, we will have a possibility to offer a highly effective long acting contraceptive method immediately after medical abortion and thereby avoid the risk of unintended pregnancy because of non-attendance for the delayed insertion.

The women will be informed regarding the study at the first visit to the family planning unit. Women can easily decline participation. The free choice to enter and also drop out of the study without having to motivate the decision will be stressed. All women will receive contraceptive counseling and information irrespective of participation in the study or not.

It is important that the individual woman does not feel forced to enter the study. If she chooses another, less effective method she will be offered counselling according to her wishes outside the study. Also, if she is not prepared to make any decision regarding further use of contraceptives this will be respected.

The women will be assured that we do not know the difference in outcome of the study in advance, so that they do not get disappointed when allotted to delayed insertion. Furthermore, it is important not to increase fear of pain related to the insertion, which may make women refrain from showing up at delayed insertion. The hypothesis that immediate insertion is less painful than delayed insertion must not turn to the belief that delayed insertion is more painful than ordinary insertion of an intrauterine device at any other time. It is therefore important that this is correctly described in the information to study subjects.

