**Sample size and calculated power**

*Justification of power calculation*

A total of 720 women will be recruited. In order to be able to show a difference of 80 percent in IUC usage in the immediate insertion group at 6 months post insertion compared to 60 percent use in the delayed group with a power of 90 percent and an alpha of 0.05 we would need to randomize 109 women in each group.

If close to 100 percent of women receive the IUC in the immediate group and there is an expulsion rate of maximum 15 percent (immediate post placental insertion after delivery has expulsion rates of 15 percent) and some women have the IUC removed a use of approximately 80 percent could be expected in the immediate group. In the delayed group fewer women are estimated to come for insertion and the expulsion rate is estimated at 5 percent.

We will stratify women in three gestational age categories ( $\leq 9$  weeks+0 days, 9weeks +1 day  $\leq 12$  weeks+0 days, and  $>12$  weeks) to make study data more internationally applicable. We will compensate for surgical procedures due to incomplete abortions and prolonged bleeding which is estimated to be needed in approximately 3-5 percent (13). We will also compensate for a 15 percent loss to follow up which is commonly seen in studies in abortion. Thus, we will randomize 240 women in each gestational strata (total 720 women). Analysis will be presented as intention to treat for all randomized women as well as per protocol for women completing the 6 month follow up (see analysis plan). Follow up at 3, 6 and 12 months will be performed by telephone/email. In women who do not attend FU electronic patient records will be searched for main and secondary outcomes (safety, pregnancy, abortion).

Women will be recruited at several sites in Sweden. Recruitment (numbers) is not expected to be equal at each site but this will be considered in the statistical analysis.

Statistical advice from statistician [name] (adjunct professor and professional medical statistician) has been sought for study design, power calculation, and analysis plan.

Randomization:

The randomization ratio between intervention and control group will be 1:1 in permuted blocks of 4-8 in three strata and per site.

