### **Variables and measures**

Primary outcome measure:

- Use of IUC at 6 months post insertion evaluated by telephone follow-up and through patient records. This will be evaluated as the proportion of women in each gestational strata (use of IUC versus no use of IUC).

Secondary outcome measures:

- Difference in the proportion of women who successfully have the IUC inserted (success versus failure),
- Expulsion rate during 12 months following insertion in both groups evaluated by telephone/email follow up at 3, 6 and 12 months post abortion (complete, partial or no expulsion. The exact day of expulsion will be noted to determine the risk of expulsion as a function of time post insertion),

- Continued use of IUC at 3, 6 and 12 months post insertion evaluated by telephone follow-up (continued use/voluntary discontinued use, involuntary discontinued use including expulsions etc) reasons for discontinuation will be recorded and subsequent use of other contraceptive methods will be noted)
- Ease of insertion according to health care provider (judged as very easy, moderately-, or very difficult)
- pain at time of insertion (women will indicate the pain before insertion, at placement of tenaculum, sound and IUC by putting a vertical mark on a 10 cm long horizontal line with a Visual Analogue Scale (VAS) from 0, indicating no pain to 10 indicating worst imaginable pain. Result will be noted in millimeters and entered into case report forms).
- Post-abortion bleeding (number of days of fresh bleeding and spotting after the abortion)
- Reasons for non-attempted insertion of IUC (change of mind, heavy bleeding, not coming for insertion, staff being unavailable etc),
- Complications (adverse events (AE) and serious AE) bleeding requiring any treatment, uterine perforations and cervical tears, infection requiring treatment with antibiotics, hospitalization for any reason, surgical procedures due to heavy bleeding, incomplete abortions, prolonged bleeding or patient request,
- Pregnancies occurring during the 12 month follow-up (planned and unplanned, wanted and unwanted, pregnancy outcomes- ectopic, miscarriage, abortion, molar, kept pregnancy),
- Acceptability of immediate and delayed insertion of IUC by asking women if they would recommend the procedure to a friend (yes/no, asked at the time of insertion and at the 3, 6 and 12 month follow up),
- Acceptability of IUC as post abortion contraception- evaluated as above,

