## **17 Statistical considerations - Sample size**

### ***17.1 Justification of power calculation***

A total of 720 women will be recruited. In order to be able to show a difference of 80 percent in IUC usage in the immediate insertion group at 6 months post insertion compared to 60 percent use in the delayed group with a power of 90 percent and an alpha of 0.05 we would need to randomize 109 women in each group. If close to 100 percent of women receive the IUC in the immediate group and there is an expulsion rate of maximum 15 percent (immediate post placental insertion after delivery has expulsion rates of 15 percent) and some women have the IUC removed a use of approximately 80 percent could be expected in the immediate group. In the delayed group fewer women are estimated to come for insertion and the expulsion rate is estimated at 5 percent.

We will stratify women in three gestational age categories ( $\leq 9$  weeks+0 days, 9weeks +1 day  $\leq 12$  weeks+0 days, and  $>12$  weeks) to make study data more internationally applicable. We will compensate for surgical procedures due to incomplete abortions and prolonged bleeding which is estimated to be needed in approximately 3-5 percent (13). We will also compensate for a 15 percent loss to follow up which is commonly seen in studies in abortion. Thus, we will randomize 240 women in each gestational strata (total 720 women). Analysis will be presented as intention to treat for all randomized women as well as per protocol for women completing the 6 month follow up (see analysis plan). Follow up at 3, 6 and 12 months will be performed by telephone/email. In women who does not attend FU electronic patient records will be searched for main and secondary outcomes (safety, pregnancy, abortion).

- Primary outcome:

The primary outcome is the difference in women with IUC use at 6 months between the two groups (immediate and delayed insertion). The results will be analyzed by Fisher's exact test. A sensitivity analysis will be performed using logistic regression taking center, parity and age into account.

- Analysis populations

The main analysis population for primary outcome will be a modified intention to treat (mITT). This population is all randomized women, with medical abortion, and follow up for main outcome recorded at 6 months. Hence, also women with no insertion and women experiencing expulsion are included in this mITT.

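### Section 6.3 asks for continued follow-up only from women who leave because of side effects or adverse events, so the 6-month outcome of other withdrawers may be missing in a way related to IUC use

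*Protocol*

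**What the plan says.** Section 6.3 of the protocol (Withdrawal criteria) concerns discontinuation from the study. It lists free drop-out, serious adverse events, and post-abortion infection before the planned insertion. It then adds: "Women who discontinue due to side effects or adverse events will be asked permission for follow up", for 12 months in total after the abortion. For a woman who simply drops out, the section states only counselling and treatment under local routines. Section 9.3 likewise refers drop-outs to general health care. Section 3.3 says that a woman's freedom to "drop out of the study without having to motivate the decision will be stressed".

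Other parts of the protocol bear on whether her outcome would still be known:

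- Section 5, Variables and measures: the primary outcome is taken from telephone follow-up and patient records. All women are contacted at 3, 6 and 12 months. Records in both groups are reviewed after 6 months, for extra visits related to the abortion and IUC-related complications.
- Section 5, Sample size and calculated power, and section 17.1: electronic records are searched for main and secondary outcomes in women who do not attend follow-up.
- Section 17.1, Analysis populations: the main population is a modified ITT of randomized women with a medical abortion and a recorded 6-month outcome. Women with no insertion or with an expulsion stay in it. A strict ITT sensitivity analysis imputes women lost to follow-up.
- Section 17, Missing data: a woman without the primary outcome is classed as a drop-out.

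Section 5 also promises: "Analysis will be presented as intention to treat for all randomized women".

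**The concern.** A special permission for one class of leavers makes sense only if leaving otherwise ends data collection. Read that way, section 6.3 makes collection of the 6-month outcome depend on why a woman left. The class not asked (change of mind about taking part, dissatisfaction with the allocation, no reason given) could well differ in IUC use from those who stay. The main analysis then leaves these women out, and the strict ITT has to impute values that nobody asked for.

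The rule is also awkward at a site. A woman may leave without giving a reason, so staff cannot always tell whether the request applies to her.

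If withdrawal is related to non-use, observed use among the remaining women is too high in any arm that loses them. The comparison is distorted when the loss differs between arms, and can be distorted even when it is equal.

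**Working it through.** **Inputs from the protocol.** Section 17.1 expects 6-month IUC use of 80% in the immediate arm and 60% in the delayed arm. With 90% power and alpha 0.05 it arrives at 109 women per group. Section 5 gives the allocation: "The randomization ratio between intervention and control group will be 1:1". There are 240 women per gestational stratum, so 120 per arm and stratum. The allowance for loss to follow-up is 15% overall, not split by arm.

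**The plan's own figure.** For two proportions with pooled variance, two-sided alpha 0.05 and no continuity correction:

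n = [1.960 × √(2 × 0.7 × 0.3) + 1.282 × √(0.8 × 0.2 + 0.6 × 0.4)]² / 0.20²
= [1.960 × 0.648 + 1.282 × 0.632]² / 0.04 ≈ 108.2, rounded up to 109.

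The stated 109 per group reproduces.

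**Effect of losing non-users.** Let d be the fraction of an arm that withdraws with no 6-month status obtained. Assume all of them are non-users, which is the extreme case. Then

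observed use = true use / (1 − d).

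The values of d below are assumptions; the protocol gives none for withdrawal.

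| Loss, delayed arm | Loss, immediate arm | Observed delayed | Observed immediate | Difference (points) |
|---|---|---|---|---|
| 0 | 0 | 60.0% | 80.0% | 20.0 |
| 5% | 0 | 0.60/0.95 = 63.2% | 80.0% | 16.8 |
| 10% | 0 | 0.60/0.90 = 66.7% | 80.0% | 13.3 |
| 15% | 0 | 0.60/0.85 = 70.6% | 80.0% | 9.4 |
| 0 | 5% | 60.0% | 0.80/0.95 = 84.2% | 24.2 |
| 15% | 15% | 70.6% | 0.80/0.85 = 94.1% | 23.5 |

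**Power in the delayed-only case.** Exact power of Fisher's test within a stratum, with 120 randomized per arm and 120, 114, 108 or 102 analysed in the delayed arm, is 91%, 80%, 60% and 34% for d = 0, 5%, 10% and 15%. If the comparison is pooled over strata (360 per arm), power at d = 10% is about 97.5%. Section 5 describes the primary outcome by gestational stratum, which supports the per-stratum reading; section 17.1 describes a plain two-group comparison.

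**Recovery from records.** If records supply the status of a fraction r of the withdrawers, d is replaced by d(1 − r). With d = 10% and half recovered, the result is the 5% row. If the withdrawers use IUC at the same rate as the rest of their arm, there is no bias at all.

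**The case against.** The strongest reply is that follow-up is already planned for everyone. The telephone and e-mail contacts are for all women, the primary outcome may come from records, and records are searched for the main outcome when a woman does not attend follow-up. All of that is true, and it means that a withdrawer may lose her outcome, not that she must. It does not close the gap. The search is worded for non-attenders, and its parenthesis names safety, pregnancy and abortion but not IUC use. The review after 6 months looks for extra visits and complications. Neither is said to continue after a woman withdraws.

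A reader might infer three stronger things, none of which the protocol supports:

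- *Women who miss the delayed insertion are lost.* They are not. Missing the visit, changing one's mind about the device, expulsion and removal are outcomes recorded by the 3, 6 and 12 month questionnaire, and section 17.1 keeps women with no insertion in the modified ITT. Only leaving the study is at issue.
- *The arms are ascertained differently by design, mainly to the detriment of the delayed arm.* Section 6.3 words one rule for both arms. A wait of 2–4 weeks against 0–48 hours makes more withdrawal before insertion plausible in the delayed arm, but no figure supports it.
- *Section 6.3 contradicts sections 3.3 and 5.* The right to leave without a reason makes the rule hard to apply but does not conflict with it. The statement in Variables and measures that "reasons for discontinuation will be recorded and subsequent use of other contraceptive methods will be noted" is about stopping the device, not leaving the study. The promised ITT is matched by the strict ITT sensitivity analysis, although imputation does not replace data that could have been requested.

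It is also fair to say that the delayed-only illustration biases against immediate insertion, so that scenario would not produce a false claim of superiority. The other rows of the table show that this protection is not general.

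**Conclusion.** The point holds in a limited form. As written, section 6.3 ties the request for further follow-up to the reason for leaving. The main analysis excludes women without a 6-month outcome, and the protocol does not say whether contact or record access continues after withdrawal. Loss related to the endpoint is therefore possible and avoidable.

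Its size and direction cannot be determined from the protocol. The illustrative range runs from a difference of 9.4 points (15% loss in the delayed arm only) to 24.2 points (5% loss in the immediate arm only), against a planned 20. It rests on assumed loss fractions, on every lost woman being a non-user, and on nothing being recovered from records. The true effect could be much smaller. The case for changing the text is that the request costs little and the data cannot be recovered later, not that a bias of a given size has been shown. It should be corrected.

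**What to change.** Reword section 6.3 so that:

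1. Removal, expulsion or non-insertion of the IUC is stated not to be withdrawal from the study. This makes explicit what sections 5 and 17.1 already imply.
2. Every woman who wishes to stop participating, in either arm and whatever the reason (none need be given), is asked the same thing: may the study make the 6-month contact about IUC use, and may it review her records to 12 months?
3. Her answer is recorded in the CRF.

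Then reconcile the follow-up and record-review text in section 5 and the record-search sentence in sections 5 and 17.1 with this. Say that they apply to withdrawn women who agree, and that IUC use is among the items extracted.

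The cost is a few sentences, a line in the consent text and a few more calls; the contacts and the record work already exist. Some women will still refuse, so the strict ITT analysis with imputation remains necessary.

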## **7 Time plan**

Planning: -March 2018

Study start: May 2018

End of recruitment: April 2020

Analysis: 2021

Report of primary outcome and Safety: 2021

## **8 Methods**

### ***8.1 Recruitment***

Women will receive written and oral information about the study from the attending physician according to the principles of the Helsinki Declaration at the first visit to the family planning clinic. They will have an opportunity to ask questions. If the woman agrees to participate and is deemed eligible she will sign informed consent in the presence of the attending physician at that consultation. This procedure will not differ between study sites. The Swedish national guidelines on medical abortion will be followed by all sites ([www.sfog.se](http://www.sfog.se)).

All centers will have a specific, GCP-certified study nurse-midwife. Participating women will receive a specific appointment for insertion of the IUC according to the wishes of the woman and the pre-defined allocation window.

## **9 Study medication**

All women will receive the assigned treatment from the study staff at each site at the time of insertion.

### ***9.1 Study Medication, dosage and administration***

The following study drugs will be used in the study;

Mirena® (LNG-IUS 52mg),

Kyleena® (LNG-IUS 19.5mg),

Jaydess® (LNG-IUS 13.5 mg),

NovaT 380® (Cu-IUD, medical device, not a drug but due to use outside indication it is included in this application, a separate application for medical device trial has been submitted)

### ***9.2 Supply, labelling, handling and storage***

The study drugs are commercially available and will be handled by Apoteket AB (Mirena®, Kyleena®, Jaydess®) and normal clinical practice (NovaT®, Cu-IUD) who will then distribute to site or local pharmacy. It will be stored and kept according to the instructions of the manufacturer. Ordered but yet not distributed study drugs will be stored at each center in a locked cabinet and only personal authorized by the investigator will have access.

The study drug will be labelled with information according to the local regulatory requirements (see the attached supplement). For each patient the batch-number and expiration date will be noted in a drug accountability list at each site.

### ***9.3 Compliance***

Compliance is part of the secondary outcomes in this trial and will be evaluated at 3, 6 and 12 months post abortion.

The IUCs can be kept or removed at the end of the study according to the wish of the enrolled woman. If the woman decides to keep the IUC after the end of study, she will be responsible

for removing it at appropriate time. In case of drop-out of the study the woman will have free access to the general health care system regarding contraceptive care. In case of expulsion or if the device has to be removed before the end of study, the woman will receive contraceptive advice and prescription by the study staff.

## **10 Concurrent/concomitant medication**

There are no restrictions for use of other medications. All concomitant medication will be recorded in the CRF.

## **11 Registration of efficacy and satisfaction**

- Difference in the proportion of women who successfully have the IUC inserted (success versus failure),
- Continued use of IUC at 3,6 and 12 months post insertion evaluated by telephone follow-up (continued use/voluntary discontinued use, involuntary discontinued use including expulsions etc) reasons for discontinuation will be recorded and subsequent use of other contraceptive methods will be noted)
- Ease of insertion according to health care provider (judged as very easy, easy, moderately, or very difficult)
- pain at time of insertion (women will indicate the pain before insertion, at placement of tenaculum, sound and IUC by putting a vertical mark on a 10 cm long horizontal line with a Visual Analogue Scale (VAS) from 0, indicating no pain to 10 indicating worst imaginable pain. Result will be noted in millimeters and entered into case report forms).
- Post-abortion bleeding (number of days of fresh bleeding and spotting after the abortion)
- Reasons for non-attempted insertion of IUC (change of mind, heavy bleeding, not coming for insertion, staff being unavailable etc),
- Pregnancies occurring during the 12 month follow-up (planned and unplanned, wanted and unwanted, pregnancy outcomes- ectopic, miscarriage, abortion, molar, kept pregnancy),
- Acceptability of immediate and delayed insertion of IUC by asking women if they would recommend the procedure to a friend (yes/no, asked at the time of insertion and at the 3, 6 and 12 month follow up),
- Acceptability of IUC as post abortion contraception- evaluated as above,

## **12 Safety registration**

- Expulsion rate during 12 months following insertion in both groups evaluated by telephone/email follow up at 3, 6 and 12 months post abortion (complete, partial or no expulsion. The exact day of expulsion will be noted to determine the risk of expulsion as a function of time post insertion),
- Complications (adverse events (AE) and serious AE) bleeding requiring any treatment, uterine perforations and cervical tears, infection requiring treatment with antibiotics, hospitalization for any reason, surgical procedures due to heavy bleeding, incomplete abortions, prolonged bleeding or patient request,
- The proportion of surgical procedures in total and for each study site (type of procedure, reasons therefore- infection, retained products of conception, prolonged bleeding etc).

